Up to 30 volunteers with type 1 diabetes will be enrolled. The upper bound is based on the expectation that some volunteers will be excluded after the screening visit and blood tests, the possibility that some qualified volunteers will not be able to complete an experiment for scheduling reasons, the possibility that some experiments may have to be discontinued before completion (e.g. due to inability to maintain IV access or subject withdrawal), and the likelihood that minor modifications to the protocol for adjustment of the GIR or the insulin infusion rate may be required during the first 2-3 experiments. Thus, it is likely that 15 clamp experiments will need to be performed to complete 12 experiments with a consistent protocol.

IV. b. Enrollment Procedures

Prospective participants may be briefed by a study staff member by phone regarding the study procedure and the inclusion and exclusion criteria. Potential volunteers may be sent an informed consent document to review by email or post.

IV. c. Consent Procedures

Potential volunteers will meet with a study physician or nurse practitioner who will explain the study and answer questions. Informed consent will be administered by an MD or NP. In the event that a volunteer is a patient of one of the study MDs or NPs, another staff MD or NP will answer questions and administer consent. If a nurse practitioner is administering the consent, a physician will be available as back-up for additional support if needed and subjects will be offered the chance to speak with a study physician if they wish.

The study physician or nurse will also answer any questions that the volunteer may have during their participation. They will share any new information in a timely manner that may be relevant to the volunteer's willingness to continue participating in the trial. The volunteers may choose to discontinue their participation at any time.

V. Study Procedures

V. a. Screening data

- Age
- Sex
- Race and ethnicity
- Urine HCG for female volunteers
- Date of diabetes diagnosis
- Medical, surgical, and social history, allergies, and review of systems relevant to inclusion and exclusion criteria
- Date of last menstrual period in female volunteers
- Medications (prescription and non-prescription) and date of last change in medication regimen
- Duration of insulin pump use
- Insulin regimen (basal rate, sensitivity factor, and carbohydrate ratio)

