- The subject will remove their own insulin pump and a primed continuous insulin infusion will be started using the insulin/saline/albumin mixture. The continuous rate will be between two-fold and four-fold higher than the mean basal insulin rate of the subject. The insulin infusion may be used to give insulin boluses if the subject is hyperglycemic at arrival to reduce the time necessary to reach steady state. Once the appropriate rate is established (with a dextrose infusion rate that is neither too low nor too high), it will remain stable throughout the experiment. For a 70 kg, 5'10" tall man with a usual basal rate of 1 u/hr, an infusion at two-fold the usual basal rate would be 17 mU/m²/min. Therefore, for a 5 ml/hr infusion 19.88 units of insulin would be added to 50 ml of saline/albumin solution (~0.4 u/ml).
- An infusion of 20% dextrose in water will be started. BG values will be measured every five minutes using arterialized blood measured with the HemoCue. The dextrose infusion will be adjusted so that the blood glucose is stabilized at 90 ± 5 mg/dl. This is expected to take approximately two hours. If the dextrose infusion rate is less than 2 mg/kg/min or greater than 8 mg/kg/min then the insulin infusion rate may be adjusted. For the 70 kg, 5'10" tall man this would correspond to 42-168 ml/hr. If this process takes longer than 3 hours, the study will be stopped.
- Blood samples (2 ml) will be processed for plasma for later insulin and glucagon measurement every 20 minutes throughout the experiment.

- Once the insulin infusion rate is established and the dextrose infusion rate has been stable for 20-30 minutes with the BG in the target range, two baseline plasma samples will be obtained and the first glucagon injection will be given.
- The order of glucagon injections will be randomized and double blinded. Neither the subject nor the provider running the experiment will know what each injection is. The study nurse will prepare the medications and label the syringes "1" and "2", for the order of injection.
- An injection of 30 mcg of Lilly glucagon or 50 mcg of Xeris glucagon (the order will be determined by block randomization) will be administered by subcutaneous injection using a syringe and a small gauge needle at a depth of less than 1 cm.

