- In the 60 minute period after the glucagon injection, the frequency of BG checks will be increased to every two minutes and blood samples will be processed for plasma at each check. After this 60 minute period, the sampling interval will return to 5 minutes and blood samples will be processed for plasma every five minutes until the GIR has stabilized for three samples, when the sampling interval will be reduced to every 20 minutes.
- The dextrose infusion rate will be adjusted to maintain the BG in the target range. Since glucagon antagonizes the effects of insulin in the liver, the dextrose infusion rate will be reduced and then increased again to baseline as the glucagon effect waxes and wanes.
- The injection site will be examined every five minutes for the first 15 minutes after injection and then every 15 minutes until 1 hour after the injection. Any local reactions will be documented, including a qualitative description and measurement of any skin reaction.
 - Dermal responses will be measured after each injection using the Draize scale, which quantifies erythema and eschar, and edema on a scale of 0-4, with 0 representing none and 4 representing severe.
- Subjects will be asked to rate the pain associated with injection on a 10 cm standard visual analog scale (VAS): 0 = no pain, 10 = worse imaginable pain
- Subjects will be asked at one hour after the injection to rate their maximal nausea during the preceding hour on a VAS: 0 = no nausea, 10 = vomiting
- Given what is known about the pharmacokinetics of glucagon given by the subcutaneous route, it is expected that it will take 60-90 minutes for the dextrose infusion rate to stabilize again.
- Once the dextrose infusion rate has remained stable for 20-30 minutes with the BG in the target range, the second glucagon injection will be given.
- A 30 mcg injection of Lilly glucagon or 50 mcg injection of Xeris glucagon (whichever formulation was not given in the first injection) will be administered by the subcutaneous route using a syringe and a small gauge needle at a depth of less than 1 cm.

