- Analysis of the initial experiments may lead to optimization of the protocol. After the glucagon injections, the GIR should decrease by at least 20% but should not be reduced to zero at any time. If the glucagon dose is not sufficient to decrease the GIR at least 20%, then lower insulin infusion rates will be used. If the glucagon dose results in the GIR being reduced close to zero, then higher insulin infusion rates will be used.

V. e. Response to adverse events

Minimal nausea was noted in clinical trials of the bi-hormonal closed-loop system in which up to 80 mcg of glucagon was given at intervals of as little as 5 minutes. The mean glucagon dose in these trials was ~1 mg over 24 hours. Therefore, we do not anticipate significant nausea associated with two 30-50 mcg doses of glucagon separated by at least one hour (total dose of 80 mcg). However, nausea is a potential side effect of glucagon.

If vomiting occurs, a study physician or nurse practitioner will be notified. If in the judgment of the provider the vomiting was likely to be due to glucagon dosing, no further glucagon doses will be given. If both glucagon doses have already been given at the time of vomiting, then the experiment will be completed if the subject is willing since completing the experiment will not involve administration of more glucagon.

V. f. Supervision by Study Staff

A study physician or nurse practitioner will order all changes to the insulin infusion and glucose infusion rates and will be on site at all times once the clamp has begun and until it is ended.

VI. Biostatistical Analysis

VI. a. Data Collected

At the time of enrollment:

- Age
- Sex
- Race and ethnicity
- Urine HCG for female volunteers
- Date of diabetes diagnosis
- Medical, surgical, and social history, allergies, and review of systems relevant to inclusion and exclusion criteria
- Date of last menstrual period in female volunteers
- Medications (prescription and non-prescription) and date of last change in medication regimen
- Duration of insulin pump use
- Insulin regimen (basal rate, sensitivity factor, and carbohydrate ratio)
- Average total daily dose of insulin in the last 30 days (from pump history)
- Height and weight
- Blood pressure
- Hemoglobin A1c
- Hemoglobin
- Creatinine and estimated GFR
- Serum Albumin
- Alanine aminotransferase (ALT)
- Fractionated metanephrines (in patients with history increasing the risk for a catecholamine secreting tumor)

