During the hyperinsulinemic-normoglycemic clamp:

- Venous BG measurements
- Timing and size of glucagon doses
- Insulin infusion rate
- Glucose infusion rates
- Plasma insulin levels every 15-30 minutes during the hyperinsulinemic-normoglycemic clamp

- Plasma glucagon levels every 2-15 minutes during the hyperinsulinemic-normoglycemic clamp
- Any adverse events, including nausea, vomiting, pain, and any local reactions to glucagon injection

VI. b. Study Endpoints

Primary endpoint analysis:

- Glucagon t_{\max} for Xeris vs. Lilly (non-inferiority)

Secondary endpoint analyses:

- Area over the curve for glucose infusion rate in the hour following a subcutaneous glucagon dose (AOC_{GIR}) for Xeris vs. Lilly
- Maximal glucose infusion rate (GIR_{\max}) for Xeris vs. Lilly
- Glucagon $t_{\frac{1}{2}\max}$ for Xeris vs. Lilly
- Quantitation of adverse events related to glucagon injection for Xeris vs. Lilly:
 - Injection pain on a 10 cm standard VAS: 0 = no pain, 10 = worst imaginable pain
 - Injection site erythema or other local reaction, maximum diameter within 1 hour of injection
 - Maximal nausea within 1 hour of injection on a 10 cm VAS: no nausea = 0, vomiting = 10

We will calculate means, median, percentages, standard deviations, standard errors, inter-quartile ranges, and 95% confidence intervals in descriptive analyses. We will use paired t-test for comparison of means. We will use multivariate regression models with repeated measurements to compare means and percentages while adjusting for patient demographics characteristics such as age, gender, body mass index, and body surface area.

VI. c. Power Analysis

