Our previous clinical study found a mean $t_{\max} \pm SD$ for Lilly glucagon after subcutaneous injection of 50 mcg of 15.8 ± 3.52 min (Appendix C). A previous pre-clinical PK/PD study in diabetic swine found no significant difference in t_{\max} between Lilly and Xeris glucagon (Appendix B). This study is powered to achieve 90% power to determine non-inferiority of Xeris vs. Lilly glucagon t_{\max} using a one-sided t-test when the margin of equivalence is 2.52 minutes (15% of the t_{\max} for Lilly glucagon in humans) and the true difference between the means of Lilly and Xeris glucagon is assumed to be 0. Therefore, the null hypothesis is that the t_{\max} of Xeris glucagon is not worse than the t_{\max} of Lilly glucagon by more than 2.52 minutes. The assumed standard deviation for each glucagon is 3.52 based on the clinical data. We assume a correlation coefficient between Lilly and Xeris glucagon within the same subject to be 0.7 in this crossover design, resulting in an SD of 2.73 in the difference between the two. The significance level (alpha) of the test is

0.05. The sample size required to achieve the designated power is 12 clamp experiments, each including one injection of Lilly glucagon and one injection of Xeris glucagon.

VII. Risks and Discomforts

There is a potential risk of nausea or vomiting in volunteers due to the administration of exogenous glucagon. The experiments, however, involve small subcutaneous glucagon doses. The recommended dose of glucagon for treatment of severe hypoglycemia in an adult with diabetes is 1000 mcg, given as a single subcutaneous or intramuscular injection. In practice, a smaller dose of 500 mcg is sometimes used initially to reduce the risk of nausea and vomiting. The total dose to be administered in our study is 100 mcg.

There is a potential risk of hypoglycemia, since exogenous insulin will be administered. Given frequent BG monitoring (every two to five minutes), corresponding adjustment of a continuous dextrose infusion, and direct supervision by an NP or MD at all times, the risk of a hypoglycemic episode leading to significant harm to volunteers is expected to be very low. A small meal will be provided to subjects after completion of the study.

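### Injection order is randomised in a crossover, but the named paired t-test has no period term, and subjects given only one injection have no stated place in the tolerability comparisons

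*Combined protocol and SAP*

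**What the plan says.** Section V.d gives both formulations in a single clamp. For the first injection, "the order will be determined by block randomization"; the second is "whichever formulation was not given in the first injection". Section VI.c assumes a correlation "within the same subject to be 0.7 in this crossover design" and powers a one-sided t-test for non-inferiority on t_max with 12 experiments.

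Section VI.b names the analysis: "We will use paired t-test for comparison of means". It also names repeated-measures regression, "adjusting for patient demographics characteristics such as age, gender, body mass index, and body surface area". Neither sentence mentions period, sequence or carry-over, and neither does any other section.

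Three other provisions matter here.
- The second injection is triggered by a dextrose rate that has been stable for 20-30 minutes: "with the BG in the target range, the second glucagon injection will be given" (Section V.d).
- If vomiting is judged likely to be due to glucagon, "no further glucagon doses will be given" (Section V.e). Vomiting is the top score, 10, on the nausea scale in Section VI.b.
- Section IV.a expects losses: "it is likely that 15 clamp experiments will need to be performed to complete 12 experiments with a consistent protocol".

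**The concern.** Randomising the order lets a first-to-second-injection shift be removed from the formulation comparison. A plain paired t-test does not remove it. In subjects given Xeris second the shift is added to the Xeris-minus-Lilly difference; in subjects given Xeris first it is subtracted. With equal numbers in each order the shift cancels from the mean but stays in the variance. With unequal numbers it also biases the mean. The covariates named for the regression are constant within a subject, so they cannot absorb it.

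For the glucose infusion rate (GIR) endpoints, the trigger for the second injection is a stable rate, not a return to the rate before the first. The two injections may therefore start from different baselines.

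The tolerability problem is separate. A subject whose second injection is withheld after vomiting has the worst possible nausea score and no pair. A paired comparison drops that subject because of the outcome being compared. Safety is part of the study hypothesis and is Aim 2 (Section II).

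**Working it through.** **Inputs from Section VI.c.** SD per formulation 3.52 min, within-subject correlation 0.7, margin 2.52 min, true difference 0, one-sided alpha 0.05, n = 12.

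**The plan's own figure.** SD of the difference = 3.52 × √(2 × (1 − 0.7)) = 2.73 min, as stated. Power from the noncentral t distribution (df = n − 1, noncentrality 2.52 × √n / 2.73) is 88.5% at n = 11 and 91.1% at n = 12. So 12 is the smallest n reaching 90%, and the sample size reproduces.

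**Adding a drift.** Let δ be the change in t_max from first to second injection, the same in both orders. The documents give no value; 1, 2 and 3 min are assumptions. The subject's Xeris-minus-Lilly difference shifts by +δ or −δ according to order. With n1 and n2 subjects in the two orders:
- bias of the paired mean = δ × (n1 − n2)/12
- at 6:6, expected sample variance of the differences = 2.73² + (12/11) × δ². At δ = 2 this gives √(7.45 + 4.36) = 3.44 min.

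**Paired t-test (df 11)**, by numerical integration over the normal mean and noncentral chi-square variance, confirmed by simulation. Type I error is evaluated at a true difference of 2.52 min.

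| Split by order | Quantity | δ = 0 | 1 | 2 | 3 min |
|---|---|---|---|---|---|
| 6:6 | power | 91.1% | 88.9% | 81.5% | 67.6% |
| 6:6 | type I error | 5.0% | 4.0% | 2.1% | 0.8% |
| 7:5 against Xeris | power | 91.1% | 84.8% | 69.9% | 46.2% |
| 7:5 favouring Xeris | power | 91.1% | 92.2% | 90.2% | 85.3% |
| 7:5 favouring Xeris | type I error | 5.0% | 6.1% | 5.1% | 3.3% |
| 8:4 against Xeris | power | 91.1% | 80% | 57% | 27% |
| 8:4 favouring Xeris | type I error | 5.0% | 9.0% | 11.3% | 11.4% |

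At 6:6, power falls below 90% once δ exceeds 0.71 min. That is 4-5% of the Lilly t_max, printed as 16.8 min in Section I.c and 15.8 min in Section VI.c. Power falls below 80% at 2.14 min.

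**Period-adjusted test** (mean of the two order-specific means, pooled within-order SD, df 10). Power is 90.8% at 6:6, 90.1% at 7:5 and 87.6% at 8:4, with type I error 5.0%, whatever δ is.

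**How likely is imbalance?** Assume 15 experiments are randomised 8:7 and 3 are lost at random. The hypergeometric distribution then gives a retained split of 6:6 in 43%, 7:5 either way in 49% and 8:4 either way in 8%. Averaged over splits and over both directions, with δ = 1/2/3 min, paired power is 88.6/80.4/66.2% and type I error 4.3/2.8/1.6%. The period-adjusted test averages 90.2% power.

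**Tolerability illustration.** Suppose 13 subjects are injected, one vomits after the first injection (score 10) and has no second, and every other score is 0. That formulation's mean nausea is 10/13 = 0.77 cm over all injections given, but 0 in the 12 complete pairs.

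**The case against.** The main objection is that no drift is documented. The plan also works to limit it: the insulin rate is held constant once established, and the second injection waits for a stable dextrose rate. A 3 min drift would exceed the whole margin. At 1 min and 6:6 the loss is 2.2 points, and averaged over the likely splits the period term gains nothing below about 0.6 min. The expected error is conservative, and 8:4 depends on losses being random. Section IV.a attributes part of the shortfall to adjustments in the first 2-3 experiments; setting aside the first 3 of 15 under blocks of 2 or 4 (block size is not stated) would rule out 8:4. All of this stands. It limits the size of the harm but does not supply the missing term.

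A second objection is that the regression's covariate list is open-ended, and such a model could hold a period term and keep single-injection subjects. It could, but the text says neither and does not make that model the primary t_max analysis.

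On GIR, Section V.d does describe the dextrose rate rising back to baseline as the glucagon effect wanes. That is expected behaviour, not a condition for the second injection.

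On tolerability, Section V.e anticipates little nausea, vomiting would still be recorded and reported as an adverse event, and no test is assigned to these endpoints individually. The illustration is deliberately extreme. The missing rule remains, and with about 12 subjects a single case matters.

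**Conclusion.** The concern holds, as something that should be changed rather than a fatal flaw. The omission is certain from the text; the size of the harm rests on a drift the documents do not give. The plan has about one point of power above its 90% target, so a drift of 0.71 min uses it up even at 6:6, and 2 min costs 9.6 points (91.1% to 81.5%). With balanced orders the paired test is unbiased and conservative. With unequal orders it is biased in a direction that depends on chance, but averaged over the likely splits type I error stays at or below 5%.

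The t_max sample size is itself protected, because the plan continues to 12 completed experiments. The tolerability comparisons are not: nothing says how a subject with one injection is counted, and the omission is related to the outcome.

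**What to change.** - Make the primary t_max analysis a crossover model with formulation, period and sequence as fixed effects and subject as a random effect. Report the one-sided 95% upper bound for Xeris minus Lilly against 2.52 min, and the number of analysed experiments in each order.
- Use the same model for the secondary endpoints. For the GIR endpoints, add that injection's pre-dose GIR as a covariate; this is a modelling choice and its small further cost is not in the figures below.
- State that nausea, pain and local reactions are analysed over all injections given, by formulation received, so that a subject whose second injection was withheld stays in the comparison.

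Only analysis wording changes; procedures and sample size do not. The period term uses one degree of freedom, plus some precision if the orders are unequal. With no drift, power goes from 91.1% to 90.8% at 6:6, 90.1% at 7:5 and 87.6% at 8:4.

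### With 12 pairs and vomiting scored as 10, the paired t-test on the nausea VAS can show weaker evidence of harm when a subject on Xeris vomits

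*Combined protocol and SAP*

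**What the plan says.** Section VI.b lists three quantitative adverse-event measures among the secondary Xeris-versus-Lilly analyses:

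- nausea: "Maximal nausea within 1 hour of injection on a 10 cm VAS: no nausea = 0, vomiting = 10"
- pain: "Injection pain on a 10 cm standard VAS: 0 = no pain, 10 = worst imaginable pain"
- local reaction: "Injection site erythema or other local reaction, maximum diameter within 1 hour of injection"

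It then gives rules that are not tied to any endpoint. The first is "We will use paired t-test for comparison of means". The second begins "We will use multivariate regression models with repeated measurements to compare means and percentages", with adjustment for demographic covariates. Medians and inter-quartile ranges appear only as descriptive summaries. No rank-based, exact or binary test is named, and sidedness is stated only for t_max (VI.c).

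Section VI.c sets the size at 12 clamp experiments, each with one injection of each formulation. Section V.e expects little nausea: "we do not anticipate significant nausea associated with two 30-50 mcg doses of glucagon separated by at least one hour". It also says that if vomiting is judged likely to be due to glucagon, "no further glucagon doses will be given".

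**The concern.** The nausea score combines a continuous scale with an event placed at its ceiling. If most subjects report little or no nausea, most of the 12 within-subject differences will be zero or small, and a vomiting case will give a difference near 10. A paired t-test divides the mean difference by its standard error, and one extreme difference inflates that standard error more than it moves the mean. A worse tolerability result can then produce a larger p-value.

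The hypothesis in Section II claims non-inferiority in terms of safety as well as PK and PD. A non-significant nausea comparison could be read as support for that claim when the reason for non-significance is that someone vomited.

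**Working it through.** **The plan's own figure.** VI.c gives an SD of 3.52 min per formulation, correlation 0.7, margin 2.52 min, true difference 0, one-sided alpha 0.05 and 90% power.

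- SD of the difference = √(2 × 3.52² × (1 − 0.7)) = 2.73, as stated.
- Noncentral-t power is 88.5% with 11 pairs and 91.1% with 12, so 12 reproduces.

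That calculation covers t_max only. Nothing is calculated for nausea.

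**Inputs for the nausea check.** From the documents: 12 pairs, the paired t-test, vomiting = 10, low nausea expected. Assumed: the individual differences (Xeris minus Lilly), because the documents give no distribution and no share of zeros; and two-sided testing.

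**Formula.** t = mean / (SD/√12), with 11 degrees of freedom. The comparator is the exact signed-rank test (sign-flip on ranks, zeros dropped). When all k non-zero differences point the same way, its two-sided p is 2 × 0.5^k.

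| Assumed differences | Mean | SD | t | t-test p | Exact p |
|---|---|---|---|---|---|
| A: six +2, six 0 | 1.00 | 1.04 | 3.32 | 0.007 | 0.031 |
| A, one +2 becomes 10 | 1.67 | 2.81 | 2.06 | 0.064 | 0.031 |
| B: six +1, six 0 | 0.50 | 0.52 | 3.32 | 0.007 | 0.031 |
| B, one 0 becomes 10 | 1.33 | 2.77 | 1.67 | 0.124 | 0.016 |
| C: 1, 1, 1.5, 2, 2, 3, six 0 | 0.88 | 1.05 | 2.90 | 0.015 | 0.031 |
| C, one 0 becomes 10 | 1.71 | 2.80 | 2.11 | 0.058 | 0.016 |
| One 10, eleven 0 | 0.83 | 2.89 | 1.00 | 0.34 | 1.00 |

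Worked line, A after the change: the sum is 5 × 2 + 10 = 20, so the mean is 1.67. The sum of squares is 5 × 4 + 100 = 120, so the variance is (120 − 20²/12)/11 = 7.88 and the SD is 2.81. Then t = 1.67/(2.81/3.46) = 2.06.

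In A the mean rises by a factor of 1.67 and the SD by 2.69. In B the factors are 2.67 and 5.31. The last row shows the limit: one dominant difference pulls t towards 1 whatever its size. The exact p stays the same or falls when the vomiting case is added.

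**Sidedness.** One-sided, A goes from 0.003 to 0.032 and C from 0.007 to 0.029, so neither crosses 0.05. B goes from 0.003 to 0.062 and does. The evidence weakens in all three; whether 0.05 is crossed depends on the data and the unstated sidedness.

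**Level and power, by simulation under assumed score distributions.** With no true difference, the two-sided t-test rejected in 0.6%, 3.8% and 5.0% of runs with 10%, 25% and 40% non-zero scores, and in 0.5–2.6% with 3% vomiting added. The exact signed-rank test rejected in 0–3.4%. In three settings with 5–10% vomiting on Xeris, power (signed-rank versus t-test) was 23% v 13%, 60% v 42% and 67% v 46%. In one setting with sparse nausea and 20% vomiting, the t-test was slightly ahead, 34% v 32%.

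**Who reaches the paired test.** Under V.e, vomiting after the first dose that is judged likely to be due to glucagon means no second injection. That subject has a score of 10 and nothing to pair it with. The reversal above therefore needs vomiting after the second dose, or vomiting not attributed to glucagon. Attributed vomiting after the first dose leaves any paired test altogether.

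**The case against.** The strongest reply is that this is a secondary comparison with no sample size or decision rule attached. Vomiting is recorded separately as an adverse event (VI.a) and adverse events go to the IRB, the DSMB and the FDA (IX.c), so a case cannot be hidden by a p-value. Aim 2 is to document adverse events, not to test them. VI.b also plans medians, inter-quartile ranges and percentages. All of this stands and limits the consequence. It does not make the t-test a sensible summary of this score, and the regression offers no rank-based or exact alternative.

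The replacement has its own weakness. Five of 12 subjects vomiting only on Xeris would give exact p = 0.0625 against a t-test p of 0.017. In example A the exact p does not respond to the change from +2 to 10. This stands too, and it is why the counts must be reported with the test. It does not tip the balance back: the signed-rank test held its level and was more powerful in three of the four simulated settings.

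Two stronger readings are tempting.

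- **False positives.** A reader might infer that the t-test also finds differences too readily, since four equal differences and eight ties give p = 0.039 against an exact 0.125. That needs four identical differences on a 10 cm VAS. Differences of 1, 1.5, 2 and 3 with eight ties give p = 0.058, and the simulations show no inflation.
- **Pain and reaction diameter.** A reader might extend the point to these. The vomiting anchor does not apply to them, and the documents nowhere say that those scores will be mostly zero.

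**Conclusion.** The point holds for the nausea VAS. With 12 pairs, low expected scores and vomiting fixed at 10, one vomiting case on Xeris can move a two-sided t-test from p = 0.007 to 0.064 or 0.124 although the mean excess has grown. The fault is a loss of sensitivity in the wrong direction.

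The size rests on assumed data, on two-sided testing for the crossing of 0.05, and on the vomiting subject having both scores. A separate gap is firmer because it follows from the text alone: a paired test omits any subject whose second dose was withheld after vomiting. The t_max analysis and its sample size of 12 are unaffected.

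**What to change.** In VI.b:

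1. For nausea, replace the paired t-test with an exact Wilcoxon signed-rank test (sign-flip on ranks). State how zeros and tied ranks are handled and whether the test is one- or two-sided.
2. Report the numbers of subjects worse on Xeris, worse on Lilly and tied.
3. Report the count of vomiting by formulation among everyone given that formulation, including subjects who received only the first dose.
4. Optionally, as a precaution, use the same test for pain and reaction diameter.
5. Leave t_max as planned.

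The cost is wording only, with no new data or subjects. The drawback is that with five or fewer non-zero pairs the exact two-sided test cannot reach 0.05 (2 × 0.5⁵ = 0.0625). The plan should say that in that case the counts carry the result and that a non-significant p-value is not evidence of equal tolerability.

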Pre-clinical studies of Xeris glucagon have been performed in a porcine model of insulin deficient diabetes (9). Xeris glucagon was compared to freshly reconstituted lyophilized glucagon (Lilly and Co., Indianapolis, Indiana) in a bioassay of the anti-hypoglycemic effects of glucagon. Yorkshire swine were treated with streptozotocin to destroy their beta cells. The insulin deficient swine were treated with subcutaneous insulin to stabilize their blood glucose (BG) in the normal range. Lilly glucagon or Xeris glucagon (10 mcg, subcutaneous injection) was then administered and blood samples were obtained every 5 minutes for 30 minutes. After re-stabilization of the BG, the other formulation was administered. There was no difference in the rise in BG after glucagon administration (ΔBG_{max}) and no difference in the mean time to maximal blood glucagon levels (t_{max}) between Lilly and Xeris glucagon formulations (9.25 ± 4.6 vs. 10.2 ± 3.6 min, $p = 0.73$) (Appendix B). There were no local complications associated with subcutaneous administration of either formulation.

I. c. Previous Clinical Studies

As part of a study examining the pharmacokinetics of insulin and glucagon after subcutaneous injection vs. intradermal injection, we performed subcutaneous injections of 50 mcg Lilly glucagon in 10 subjects and measured plasma glucagon levels every five minutes for 55 minutes after injection. The mean $t_{max} \pm SD$ was 16.8 ± 3.52 minutes (Appendix C). The somewhat slower absorption of glucagon in human subjects relative to swine is consistent with similar findings for insulin lispro, which is also absorbed more quickly in swine.

I. d. Rationale and Potential Benefits

Xeris Pharmaceuticals is currently conducting a study under Investigational New Drug (IND) 115091 using their non-aqueous synthetic glucagon formulation to examine safety, pharmacokinetics and efficacy as compared to Lilly glucagon in healthy volunteers. Subjects in this study received 0.5 and 1.0 mg doses of Xeris glucagon, compared to 1.0 mg of Lilly glucagon. Pharmacokinetics data is not yet available. Blinded clinical safety data has shown that all adverse events were mild to moderate in nature, and known effects of rescue doses of glucagon. In addition, Xeris recently received approval of IND 119733 to test mini-dose glucagon, with doses up to 0.3 mg. See the Investigator's Brochure in Appendix A for more information.

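### Does the conflict between 15.8 and 16.8 min for the Lilly t_max mean undermine the 2.52 min non-inferiority margin?

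*Combined protocol and SAP*

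**What the plan says.** Section I.c (Previous Clinical Studies) describes the investigators' earlier human study: "we performed subcutaneous injections of 50 mcg Lilly glucagon in 10 subjects". It reports that the mean t_max "was 16.8 ± 3.52 minutes (Appendix C").

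Section VI.c (Power Analysis) reports the same quantity "after subcutaneous injection of 50 mcg of 15.8 ± 3.52 min (Appendix C"). It then sets the non-inferiority limit: "margin of equivalence is 2.52 minutes (15% of the t_{\max} for Lilly glucagon in humans"). The limit appears again, in minutes, in the sentence on the null hypothesis: "of Lilly glucagon by more than 2.52 minutes".

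The other inputs in VI.c are an SD of 3.52 min for each formulation, a within-subject correlation of 0.7, a resulting SD of the paired difference of 2.73 min, a true difference of zero, a one-sided t-test at alpha 0.05 and a 90% power target. The result is 12 clamp experiments, each with one injection of each formulation.

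**The concern.** Drug, dose, route, SD and cited appendix agree between the two sections, and only the mean differs, by 1.0 min. At least one of the two printed means must be wrong.

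This deserves a check because t_max non-inferiority is the primary endpoint (VI.b) and the only reason given for the size of the margin is that it is 15% of the Lilly mean. The mean that opens the VI.c paragraph does not give the margin stated later in that paragraph. If the margin had been built on a wrong reference value, the test would be more lenient than its label, or the trial slightly underpowered for the margin intended.

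**Working it through.** **Inputs.** Lilly mean 16.8 min (I.c) or 15.8 min (VI.c). From VI.c: margin 2.52 min, SD 3.52 min per formulation, correlation 0.7, true difference 0, one-sided alpha 0.05, power 90%, n = 12.

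**Step 1: which mean fits the margin.**

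- 0.15 × 16.8 = 2.52 min, equal to the stated margin.
- 0.15 × 15.8 = 2.37 min, which is not the stated margin.
- 2.52 / 15.8 = 15.9%.
- Working backwards, 2.52 / 0.15 = 16.8. A 15% margin that rounds to 2.52 needs a mean between 2.515 / 0.15 = 16.77 and 2.525 / 0.15 = 16.83.

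So the margin and its label point to the value in I.c.

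**Step 2: reproduce the plan's sample size.** The SD of the paired difference is 3.52 × √(2 × (1 − 0.7)) = 2.727 min, against 2.73 stated. For a paired one-sided t-test with true difference zero, the noncentrality parameter is margin × √n / SD of the difference, with n − 1 degrees of freedom. At n = 12 and margin 2.52 it is 2.52 × 3.464 / 2.73 = 3.20.

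| Margin (min) | n | Power |
|---|---|---|
| 2.52 | 11 | 88.5% |
| 2.52 | 12 | 91.1% |

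Twelve is the smallest n that reaches 90%, so the plan's figure is reproduced. The unrounded SD of 2.727 moves the power at 12 only to 91.2%.

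**Step 3: where the mean enters.** The formula contains the margin, the SD of the difference, alpha and n. The Lilly mean is not in it. Nor is it in the analysis, which compares the paired difference in t_max with a limit fixed in minutes.

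**Step 4: the unfavourable case.** Suppose 15.8 were correct and the 15% rule took precedence over the stated minutes. The margin would be 2.37 min and the noncentrality at n = 12 would be 2.37 × 3.464 / 2.73 = 3.01.

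| Margin (min) | n | Power |
|---|---|---|
| 2.37 | 12 | 87.9% |
| 2.37 | 13 | 90.35% |

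The cost would be 91.1 − 87.9 = 3.2 percentage points of power, or one more clamp experiment.

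**Step 5: scale of the discrepancy.** Assuming one t_max value from each of the 10 earlier subjects, the standard error of the reference mean is 3.52 / √10 = 1.11 min. The 1.0 min difference between the printed means is smaller than that, and it moves a 15% margin by 0.15 × 1.0 = 0.15 min.

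**The case for a change.** The best case for acting is that a non-inferiority margin needs a traceable basis, and this one has a single stated basis that fails in the section where it is used. Appendix C is not part of the text available here, so 16.8 is an inference. If the appendix showed 15.8, the margin would have to be called about 16% of the Lilly value, or be cut to 2.37 min with the power loss in Step 4. The correction itself costs almost nothing.

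The mismatch and the arithmetic stand. The consequence does not. The unfavourable case needs two things together: that 15.8 is the true mean, although 2.52 was evidently computed from 16.8, and that the percentage overrides a threshold given twice in minutes. The plan supports neither. A digit misread when the document was converted to text would also produce this pattern.

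Two further arguments should not be used.

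- The sample size of 12 is not separate evidence for 16.8. It follows from the margin in minutes, and under the 15% rule any mean from about 16.4 min (2.464 / 0.15) keeps 90% power at 12.
- Section I.c says glucagon was measured "in 10 subjects and measured plasma glucagon levels every five minutes for 55 minutes after injection", so one might argue that ten nominal peak times must average to a multiple of 5 / 10 = 0.5 min, which neither mean is. That assumes exactly one profile per subject read at nominal times, which I.c does not state. With 20 profiles, as an illustration, 15.75 and 16.75 are possible and round to 15.8 and 16.8. The argument also counts equally against both values, so it cannot choose between them.

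**Conclusion.** This is a clerical inconsistency in background text, most likely a one-digit slip in VI.c, and it calls for no change to the plan. The primary threshold remains 2.52 min, the sample size remains 12, and power remains about 91% against a target of 90%. An analyst following the plan would run the same test and reach the same conclusion whichever mean is printed. Anyone who wants the basis of the 15% finds 16.8 in I.c, or recovers it from VI.c by dividing 2.52 by 0.15. Agreeing the two numbers with Appendix C is a matter for proofreading.

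The conclusion rests on reading the margin as the absolute value that VI.c states twice, and on the plan's own SD, correlation and zero true difference. It does not depend on which mean is correct. If the sponsor instead treated the 15% as binding and the mean were 15.8, the effect would be limited to 87.9% power at 12 experiments.
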